### SUCCESS CRITERIA AND BARRIERS

[name], in collaboration with each WP lead, will be responsible for identifying and managing risks and potential barriers. They will undertake a formal risk assessment and maintain a risk register. Risk or barriers to delivery will be a standing item for all team meetings to ensure the early identification of any issues arising, and to enable us to take timely remedial or mitigating action. If difficulties were not rapidly resolvable, we would inform the Project Steering Committee and our grant manager at NIHR as appropriate. The following are the key areas of risk identified to date:

- 1. **Challenging timescale**; this programme has four interrelated WPs, which creates a time-pressure from the outset; the development of eBPI (WP2) is particularly crucial to later work, but mitigated by the fact that [name] and [name] are already engaged with Acteon Communications LLP and preliminary work has already begun. Reviewing our progress against key goals at team meetings will quickly detect unexpected delays. We are an experienced team and with strong project management anticipate being able to stick to our proposed timeline which is realistic and adequately resourced.
- 2. **Failure to recruit and retain participants** across all WPs; all co-applicants have experience and professional networks that can be brought to bear to support recruitment. Our scoping work suggests enthusiasm to access eBPI in both NHS trusts, and the team has considerable expertise in clinical trials among young people with poor mental health so have many effective strategies to boost recruitment and prevent attrition.
- 3. **Managing the diffused team;** [name] will have oversight of all WPs as the Programme Lead, and our collaboration is built on a network of established and successful working relationships. We have clearly delineated roles and responsibilities and will use frequent clear communication in and between meetings to ensure the dispersed nature of our project team does not impede the smooth delivery of this research. Recording of remote meetings and meeting minutes will be circulated promptly to inform those who were unable to attend and to record key decisions and outputs.

- 4. **Illness or change of role of a senior team member:** We have engaged a broad base of experts in mental health with overlapping skills, which creates potential resilience in case of changes within the collaboration.
- 5. **Risk to self or others or child safe-guarding concerns:** These are likely to emerge during the delivery of eBPI but could emerge in any WPs during interviews or questionnaire completion. Research staff will all be trained to follow clear standing operating procedures agreed with the Project Management Group and Steering committee. These will be written guidelines that describe the procedures that should be taken when disclosures are made. If appropriate, relevant information will be fed into the CYPMHS processes and reported as a potential Serious Adverse Effect. They will be noted centrally to allow any patterns to be identified.
- 6. **Data security or ethics breach:** Our protocol and data management will be supported by explicit standard operating procedures and mandatory staff training on data governance and ethical research. There will be rapid reporting and review of any breaches involving the Project Steering Committee and NIHR as appropriate.
- 7. **Withdrawal of a clinical site from WP3:** We consider this unlikely as there are strong links between the co-applicants across sites leading to successful delivery of complex projects. Finally, [name], [name] and [name] have extensive collaborative child mental health networks and we are confident that if required, we could encourage an additional site (s) to join the study.

**Progression** to definitive trial would require the following success criteria to be met:

- Recruitment (target 40 per trust, 8 per clinic, total 80) progression recommended if a minimum of 60 were recruited.
- Engagement with eBPI in the treatment arm (target 40); minimal clinically relevant engagement will be assumed to be 2 activitations of eBPI but this will be refined during WPs 1 to 3 and reviewed after WP4. Progression would be recommended if 65% of those randomised engaged (this would be between 19 and 26 depending on recruitment figures).
- Retention (target 70 or 87%) progression recommended if **75% or more (ie 60 if 80 recruited)** were retained at 18 weeks:

Progress to a definitive RCT would not be viable if our pilot study does not collect sufficient data to inform the full protocol. Specifically: if fewer than 50 participants were recruited; fewer than 30% of those recruited engaged; or fewer than 50% were retained. We plan an interim review once recruitment is completed (end of month 26), when approximately half of the sample will have progressed to the post treatment data collection at 10 weeks and a quarter to 18 weeks. This would provide time for us to consult stakeholders, the clinical trials unit and our trial steering committee to devise strategies that might improve recruitment, engagement, and retention by the end of the trial.

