All participating clinics have standardised procedure for supporting young people who are on the waiting list, which will be available to all participants. Young people are provided with contact information for a duty clinician who they can contact should they experience worsening mental health or a crisis. We will explore if and how the eBPI tool may send relevant information to duty clinicians in this phase and develop a standardised operating procedure for flagging concerns and supporting young people that can be carried into WP4.

WP4 Pilot trial of eBPI versus waiting list as usual with embedded process and economic evaluation; lead [name]: months 21 to 32

The WP4 pilot trial aims to evaluate research measures, processes, and engagement with eBPI to provide essential information to support the design of an adequately powered definitive RCT, as well as data completeness of outcome measures. Our specific objectives are:-

• To estimate recruitment, retention and engagement with eBPI

- To explore whether higher intensity data collection, which would allow us to date response and explore mechanisms of change in a larger study, influence the completeness of data.
- To collect data on variance of depressive symptoms in the waiting list population (we can
  find no existing examples in the literature) to support the power calculation for the
  definitive trial.

The trial will **include** young people aged 12 to 17 years recruited from the CYPMHS waitlist for treatment because of low mood or depression. Eligibility commences from the moment of allocation to the waiting list and persists until a young person chooses to leave the waiting list or is offered a treatment by CYPMHS. From prior RCT research we can infer that the median age of wait list participants in scope for eBPI will be 15yrs and 3 months and 70% will be female sex as assigned at birth (2). We have no initial **exclusion criteria** but anticipate that some may emerge during WP1 and 3. Young people in crisis are likely to come off the waiting list so by definition will no longer be eligible. Some young people may deteriorate whilst part of the study and require active treatment from CYPMHS, which we will monitor in terms of safety and numbers to inform sample size calculation for a definitive trial. We would not withdraw access to eBPI should this occur, unless advised to do so by the treating CYPMHS practitioner. Such discussions will be carefully recorded and monitored.

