Norwich CTU will randomly allocate young people to eBPI (n=40) or waiting as usual (n=40) at the individual level. Clinician support as provided by local CYPMHS policy will be available to both groups throughout. Because of the sex difference in the prevalence of depression in young people and our relatively small sample, we propose to stratify randomisation by sex assigned at birth so that we ensure some boys are recruited to each arm. We will stress to participants and participating clinics that **eBPI will be provided as part of, rather than instead of, being on the waiting list** because fear of losing their place is a common reason reported for not engaging in such interventions (44). Within each treatment group, we will additionally randomise to low intensity (baseline, post intervention and follow up; n=40) and higher intensity data collection (basic schedule plus fortnightly short version of the Moods and Feelings Questionnaire (MFQ; 45) until week 10; n=40; see Figure 3). The follow up schedule will remain unchanged for those who choose to come off the waiting list or are offered and accept treatment, unless they withdraw themselves from the study.

Figure 3 Data Collection Schedules

Low intensity data collection n=40

High intensity data collection n=40

We propose to recruit between 8 and 10 young people per clinic to generate a total of 80 and anticipate that recruitment will be completed within three months (months 21 to 24; 3 to 4 young people per clinic per month). The eBPI intervention will last for eight weeks (starting month 22 and completing by the end of month 27 depending on recruitment date and allowing two weeks after baseline to randomise and set up eBPI for the intervention arm. Data from our own trials and examination of current wait lists in two collaborating CYPMHS suggests that 95% of those waiting accept treatment when initially offered. Given 30% only attend one session (4) while 1 in 5 CYPMHS patients who entered the IMPACT trial only had a therapy 'dose' of 2 sessions, we estimate that between 15 to 30% will respond to eBPI and choose to leave the waiting list compared to those waiting as normal. This sample size is sufficient to provide data to test these assumptions.

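### The 18-week retention progression rule pools the two arms, so it can be met despite heavy loss confined to the eBPI arm and may miss differential attrition

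*Protocol*

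**What the plan says.** The Success Criteria and Barriers section sets three progression criteria: recruitment, engagement and retention. The retention criterion reads "Retention (target 70 or 87%) progression recommended if" "75% or more (ie 60 if 80 recruited") "were retained at 18 weeks". The same section says a definitive trial would not be viable if "fewer than 30% of those recruited engaged; or fewer than 50% were retained".

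The WP4 section supplies the denominator: "Norwich CTU will randomly allocate young people to eBPI (n=40) or waiting as usual (n=40) at the individual level". It lists among the pilot's objectives "To estimate recruitment, retention and engagement with eBPI", and says of the effect on waiting-list choice that "we estimate that between 15 to 30% will respond to eBPI and choose to leave the waiting list compared to those waiting as normal". It also says that the follow-up schedule stays the same for participants who come off the waiting list or accept treatment, unless they withdraw from the study.

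Engagement is the only criterion read on the eBPI arm alone: 65% of those randomised to it, with two activations as the provisional minimum. No criterion for retention by arm, and no limit on the difference between arms, appears in the protocol.

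**The concern.** The pilot is meant to decide whether a definitive trial comparing eBPI with waiting as usual on the Moods and Feelings Questionnaire (MFQ) is warranted. The retention failure that most directly threatens that comparison is unequal loss between the arms, particularly if those lost differ in outcome from those who stay. A rule whose only input is total retained over total recruited cannot distinguish equal from unequal loss.

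The arms may well be followed up under different circumstances. The protocol expects more eBPI participants to leave the waiting list, and its Participant vulnerability section says that leavers need additional safety procedures agreed with local services. Whether they still complete the 18-week measures is something the pilot could show, but the progression rule does not ask.

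**Working it through.** **Inputs.** 80 randomised, 40 per arm (WP4). Retention target 70, 'go' at 75%, stop below 50%, all at 18 weeks (Success Criteria and Barriers). Minimum recruitment for progression 60 (same section). MFQ minimum clinically important difference 5 points (Measures). Retention by arm is not stated, so every per-arm rate below is an assumption. 'Go' means that the retention criterion is met; the recruitment and engagement criteria apply as well.

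**Step 1: reproduce the plan's figures.** 0.75 × 80 = 60, as stated. 70/80 = 87.5%, printed as 87%. Sixty of 80 is a total over both arms, so the rule is pooled. The stop line on the same base is fewer than 0.50 × 80 = 40.

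**Step 2: which splits pass.** Control participants needed = 60 − eBPI participants retained.

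| eBPI retained | eBPI loss | Control needed |
|---|---|---|
| 30/40 | 25% | 30/40 (75%) |
| 26/40 | 35% | 34/40 (85%) |
| 24/40 | 40% | 36/40 (90%) |
| 22/40 | 45% | 38/40 (95%) |
| 20/40 | 50% | 40/40 (100%) |
| 18/40 | 55% | 42/40, impossible |

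With 60 recruited (30 per arm, 45 needed), the pattern is the same: 18/30 in eBPI needs 27/30 in control, and 15/30 needs 30/30.

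**Step 3: the stop line.** 0/40 eBPI with 40/40 control totals 40, exactly 50%, so the stop is not triggered. The 'go' line fails, since 40 is below 60.

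**Step 4: how often the pooled rule passes.** P('go') = P(X + Y ≥ 60), with X ~ Bin(40, eBPI retention) and Y ~ Bin(40, control retention), computed exactly. The last column adds the condition X ≥ 28 and Y ≥ 28 (70% in each arm).

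| True eBPI | True control | Pooled rule | With 28/40 in each arm |
|---|---|---|---|
| 60% | 75% | 0.09 | 0.06 |
| 60% | 80% | 0.19 | 0.09 |
| 60% | 85% | 0.35 | 0.12 |
| 60% | 87.5% | 0.45 | 0.12 |
| 60% | 90% | 0.56 | 0.13 |
| 60% | 95% | 0.77 | 0.13 |
| 80% | 80% | 0.89 | 0.86 |
| 87.5% | 87.5% | 0.999 | 0.998 |

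**Step 5: illustration of possible bias (assumption throughout).** Suppose that a complete-case analysis is used and that, in each arm, those lost differ from those retained by k MFQ points in the same direction. The completers' mean in an arm is then off by (loss fraction × k), and the bias in the comparison is the difference in loss × k. For 24/40 v 36/40 this is (0.40 − 0.10) × k = 0.30k: 0.6 points at k = 2, 1.5 points at k = 5 (30% of the 5-point difference) and 3.0 points at k = 10. The protocol fixes neither k nor a complete-case analysis.

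**The case against.** Much can be said for the protocol.

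- Passing with 40% eBPI loss needs at least 90% control retention, above the protocol's overall target of 87.5%. Passing with 50% loss needs every control participant. Beyond 50% no 'go' is possible. A reader might infer that the rule generally gives a 'go' whenever the eBPI arm loses 40% or more; Step 2 shows that it does not.
- A reader might take the expected 15 to 30% leaving the waiting list as evidence of differential attrition. The documents do not support that. Leaving is a secondary outcome, follow-up continues unchanged for leavers, and measures are to be completed on a web-based tool or on paper rather than through the waiting list.
- A reader might conclude that the definitive trial would be biased. That requires the pattern to recur, the loss to be related to outcome and the analysis not to deal with it. The protocol establishes none of these.
- The stop line addresses whether there are enough data to inform the full protocol, and when it fails to trigger at 0/40 v 40/40 the 'go' line still fails.
- Retention is also an objective to be estimated, is monitored by the clinical monitoring committee and is considered at an interim review. Reporting by arm is commonly left to the statistical analysis plan.

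These points limit the strength of the claim but do not remove it. An unchanged schedule does not guarantee completed 18-week measures. The engagement criterion counts use of the tool, so a participant can engage and then be lost. Neither the committee nor the interim review is stated to examine retention by arm, and neither alters the numerical rule, which the protocol itself fixes.

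**Conclusion.** The point holds in limited form. The retention criterion is pooled, can be met with 24/40 eBPI and 36/40 control retained (at the extreme 20/40 and 40/40), and so may not detect differential loss that could bias a definitive trial.

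The splits that pass follow from the protocol's own numbers. The probability of a pass does not: at an assumed 60% true eBPI retention it runs from 0.09 to 0.77 as assumed control retention goes from 75% to 95%, and nothing in the protocol says where in that range the trial will fall. The calculation also assumes full recruitment and independent participants. This is a cheap improvement to a progression rule, not an error that invalidates the pilot.

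**What to change.** In Success Criteria and Barriers:

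1. Keep the pooled 75% line. Make the retention 'go' unconditional only if each arm also retains at least a stated minimum at 18 weeks, for example 70% (28/40, pro rata if fewer are recruited, so 21/30 with 60 recruited). If either arm falls short, review retention by arm before deciding on progression.
2. Apply the 50% stop line to each arm as well as to the total.
3. Report retention by arm with a 95% confidence interval for the difference, here or in the statistical analysis plan.

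The 70% level is a proposal for the team to confirm. It guards the level in each arm rather than the gap: 38/40 v 28/40, a 25-point difference, would still pass. The reported difference should therefore be read alongside it.

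The cost is a few phrases and no new data. Slightly fewer unconditional 'go' decisions would follow when the arms are alike (0.999 to 0.998 at 87.5% in both, 0.89 to 0.86 at 80% in both), against a fall from 0.56 to 0.13 at 60% eBPI and 90% control.

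### The engagement stop line is set on all those recruited while the go line is set on the eBPI arm, and the lower go count of 19 misses its own 65%

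*Protocol*

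**What the plan says.** Under Success Criteria and Barriers, the protocol makes progression to a definitive trial depend on recruitment, engagement and retention, each with a go level and a stop level.

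- **Recruitment go level:** "progression recommended if a minimum of 60 were recruited", against a target of 80.
- **Population for engagement:** "Engagement with eBPI in the treatment arm (target 40".
- **Engagement go level:** "Progression would be recommended if 65% of those randomised engaged (this would be between 19 and 26 depending on recruitment figures".
- **Stop levels for all three criteria:** "if fewer than 50 participants were recruited; fewer than 30% of those recruited engaged; or fewer than 50% were retained".
- **Definition of engaged:** two activations of eBPI as a working minimum, "but this will be refined during WPs 1 to 3 and reviewed after WP4".

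The WP4 section gives the allocation: "Norwich CTU will randomly allocate young people to eBPI (n=40) or waiting as usual (n=40) at the individual level".

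**The concern.** Only participants allocated to eBPI can engage with it. The go criterion respects this, because it names the treatment arm. The stop rule does not: its base is those recruited, and the other uses of that word in the section (80 as the target, 60 as the go minimum, 50 as the recruitment stop level) all count both arms. The two halves of one criterion therefore appear to use different denominators, and the stop rule gives no counts from which the intended one could be inferred.

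Engagement is one of three criteria that decide whether a full trial is viable. If the committee and the trial team read the stop line differently, the same pilot result could be a stop for one and an intermediate result for the other. Settling the meaning after the results are known would make the decision depend on the data.

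A smaller inconsistency affects the go rule: the lower of its two quoted counts does not reach the stated percentage at the recruitment minimum.

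**Working it through.** **Inputs.** Allocation 40 and 40 (WP4 section). Recruitment target 80 and go minimum 60, go level 65% with counts 19 to 26, stop level 30% of those recruited (all from Success Criteria and Barriers). I assume exact 1:1 allocation at every recruitment total, so 60 recruited gives 30 in the eBPI arm.

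**Step 1: reproduce the go counts.** Count = 0.65 × denominator.

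- eBPI arm: 0.65 × 40 = 26; 0.65 × 30 = 19.5, quoted as 19.
- All randomised: 0.65 × 80 = 52; 0.65 × 60 = 39. These do not give 19 to 26, and 52 exceeds the 40 who are offered eBPI.

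So the go rule uses the eBPI arm, although its phrase for the denominator does not say so.

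**Step 2: check the lower go count.** 19/30 = 63.3%, below 65%. 20/30 = 66.7% is the first count that passes. The upper count is exact: 26/40 = 65.0%.

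**Step 3: stop line under each reading.**

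| Recruited | eBPI arm | 30% of all recruited | As share of eBPI arm | 30% of eBPI arm |
|---|---|---|---|---|
| 80 | 40 | 24 | 60% | 12 |
| 60 | 30 | 18 | 60% | 9 |

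The zone between stop and go is then 24 to 25 of 40 on the literal reading and 12 to 25 of 40 on the arm reading. At 30 in the arm, with 20 as the go count, it is 18 to 19 or 9 to 19.

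**Step 4: how far the readings differ.** Let X be the number engaged among 40, binomial with true engagement p. The chance of a stop is P(X < 24) on the literal reading and P(X < 12) on the arm reading.

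| True engagement | Stop, all recruited | Stop, eBPI arm |
|---|---|---|
| 50% | 87% | 0.3% |
| 55% | 68% | 0.04% |
| 65% | 20% | below 0.01% |

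**Step 5: effect of 19 against 20 as the pass mark, with 30 in the arm.** At p = 55%, P(X ≥ 19) = 23% and P(X ≥ 20) = 14%. At p = 60%, the figures are 43% and 29%.

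**The case against.** The best defence is that the denominator is clear from context. The engagement criterion is introduced for the treatment arm, and the stop rule restates the same three criteria in shorthand. The go rule is worded just as loosely, yet its counts show that the eBPI arm is meant. The stated reason for stopping is that the pilot would yield too little data to inform the full protocol, which hardly describes 23 of 40 engaging (57.5%). This makes 12 of 40 the likely intent. It follows that the 68% and 20% stop probabilities measure the distance between two readings; they are not the expected error of the rule as it would probably be applied. That stands. What it does not answer is that the stop rule uses a word that elsewhere in the section means both arms, and gives no count to correct it.

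On the count of 19, the operative rule is the percentage and the counts are illustrative. The failure also needs exactly 30 in the arm: with 29, 19/29 = 65.5% passes. This too stands, and the slip is one participant.

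A reader might also infer that the definition of engaged is left open until the WP4 results are known. The document does not support that. It says "minimal clinically relevant engagement will be assumed to be 2 activitations of eBPI but this will be refined during WPs 1 to 3 and reviewed" once the pilot is over, so a numerical definition exists and its refinement precedes the pilot. The later review can naturally be read as serving the definitive trial, and nothing says that the pilot would be re-scored. The sentence simply does not state what that review covers.

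**Conclusion.** The engagement thresholds are inconsistent as written. Read literally, the stop line is 24 of 80, which is 60% of the eBPI arm and almost at the go line of 26. The probable intent is 12 of 40, and the stop rule contains nothing that decides between them. The choice matters across plausible engagement rates: at 55%, it moves the chance of a stop from under 0.1% to 68%. A reader might conclude that the sponsor has deliberately chosen a wrong denominator; the text shows only that the wording is inconsistent.

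The lower go count is a separate, small rounding error in a pass mark: 20, not 19, when 30 are in the eBPI arm.

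These results rest on 1:1 allocation at each recruitment total and, for the probabilities, on independent binomial engagement. The count results need only the first assumption.

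**What to change.** - State both engagement rules on participants randomised to eBPI. Go at 65% or more: 26 of 40, or 20 of 30. Stop below 30%: fewer than 12 of 40, or fewer than 9 of 30. If 30% of both arms together really was intended, the protocol should say so and give the count.
- Change the go range to 20 to 26, noting that it assumes 1:1 allocation and that the percentage governs if the arm size differs.
- As a minor clarification, say that the definition of engaged as refined in WPs 1 to 3 is the one used for the WP4 progression decision, and that the review after WP4 informs only the definitive trial.

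The cost is a few sentences in one section, with no extra data and no design change. The edits should be made before WP4 engagement results are seen.
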